As a consequence, an acellular dermal matrix (ADM) allograft has been used as a SCTGs replacement. The ADM allograft is obtained from an allograft donor skin and produced by a carefully controlled process that removes the epidermis and dermis cells without altering the extracellular matrix structure which provides the basis for cellular in-growth and subsequent tissue remodelling⁽⁹⁾. However, these grafts are very thin due to the manufacturing process and showed an increased shrinkage rate⁽¹⁰⁾.

Besides, histological analysis of tissue augmented with ADM did not resemble native oral soft tissue, but had a more scar-like appearance⁽¹¹⁾.

Recently, Amniotic Chorion membrane (ACM) has been proposed to augment keratinized tissues around teeth and dental implants. ACM is the inner most lining of the fetal membrane that is in contact with the developing fetus⁽¹²⁾. The ACM has numerous advantages owing to its structure and composition. The extracellular matrix comprises collagen Types I, III, IV, V, and VI and cell-adhesion bioactive factors, such as fibronectin and laminin⁽¹³⁾.

Collagen is well tolerated and bioabsorbable, has haemostatic properties, and encourages migration of adjacent autogenous connective tissue. Fibronectin is involved in many cellular processes, including tissue repair, blood clotting, cell migration, and adhesion⁽¹⁴⁾.

Laminin and Laminin-5 has a high affinity for binding epithelial cells in contrast to traditionally available membranes⁽¹⁵⁾. This biological factor allows the ACM to be left exposed to the oral environment. It is believed that the antibacterial property of ACM is related to the presence of lysozyme present in amniotic fluid⁽¹⁶⁾.

According to Talmi and coworkers⁽¹⁷⁾, lysozyme is a powerful bactericidal enzyme in high concentration in ACM, and it acts against many gram-negative microorganisms. Some studies have suggested that ACM is relatively well tolerated when used as a self-graft^(18, 19).

It has been also proven that the ACM has a potential for regeneration in periodontology as the matrix of the chorion contains abundant growth factors, such as keratinocyte growth factor, basic fibroblast growth factor,

and transforming growth factor- β , that promote periodontal regeneration and provide a natural environment for accelerated healing⁽²⁰⁾. It was used in socket preservation, guided tissue regeneration and guided bone regeneration. Furthermore, the ability of this allograft to self-adhere eliminates the need for suturing^(15, 21).

To the best of our knowledge, there is still a scarcity of literature evaluating the feasibility of ACM. Furthermore, there have been no studies conducted to evaluate the clinical efficacy using SCTG compared to ACM simultaneously with dental implant placement.

The hypothesis states that using ACM membranes will produce equivalent results in terms of PMT enhancement around dental implants in comparison to SCTG graft in humans. The present study will be performed to compare and evaluate clinically and radiographically the soft tissue healing around dental implants augmented with subepithelial connective tissue graft versus Amnion Chorion Membrane.

Aim of the work

The objective of this study will be to assess the efficacy of the peri-implant mucosal thickness enhancement following either subepithelial connective tissue grafts or Amnion Chorion Membrane placed simultaneously with dental implant placement.

Materials and Methods

Study design:

A Randomized clinical study, single blinded, with equal randomization, active controlled, with Allocation ratio 1:1.

Study setting:

The research will be carried out in the Periodontology clinic, Faculty of Dentistry, Tanta University.

Ethical consideration:

The Purpose of the present study will be explained to the patients and informed consent will be obtained according to guidelines on human research adopted by the Research Ethics Committee (REC) at Faculty of Dentistry, Tanta University.

Sample size calculation:

The minimal sample size is calculated based on a previous study aimed to evaluate the early volumetric changes after buccal soft tissue contour augmentation around implants with a porcine collagen matrix (CM) versus the subepithelial connective tissue graft (SCTG) from the palate.⁽²²⁾ Schmitt et al. (2021)⁽²²⁾ reported that the mean soft tissue thickness increase (mm) in the buccal contour after 6 months was 0.30 ± 0.16 mm (CM) and 0.80 ± 0.61 mm (SCTG). The sample size was calculated to detect difference in increase in the soft tissue thickness. Based on Schmitt et al. (2021)⁽²²⁾ results, and adopting a power of 80% ($\beta=0.20$) to detect a standardized effect size in increase in the soft tissue thickness (primary outcome) of 1.121, and level of significance 5% (α error accepted =0.05), the minimum required sample size was found to be **11 patients per group** (number of groups=2) (**Total sample**

size=22 patients)^(23, 24). After adjustment for a dropout rate of 10%, the sample size was increased to **13 patients per group** (number of groups=2) (**Total sample size=26 patients**).⁽²⁵⁾

Software:

The sample size was calculated using G Power version 3.1.9.2⁽²⁶⁾. The equation is:

$$N = \frac{(r + 1)(Z_{\alpha/2} + Z_{1-\beta})^2 \sigma^2}{rd^2}$$

Where Z_a is the normal deviate at a level of significance and $Z_{1-\beta}$ is the normal deviate at $1-\beta\%$ power with $\beta\%$ of type II error

Sites selection:

Twenty-six sites that are indicated for peri-implant mucosal augmentation at the time of implant placement will be selected from the Periodontology Clinic, Faculty of Dentistry, Tanta University. Participants will be randomized to the control (subepithelial connective tissue graft) or test (amniotic chorion membrane) group. To include the patients in this study their written consent will be obtained, and all the procedure will be explained before the treatment.

Inclusion criteria:

- Patients with good systemic health with no contraindication for periodontal surgery.
- No history of any medications in the previous 6 months that may interfere with periodontal tissue health or healing.
- Ability to maintain good oral hygiene as evidenced in recall visits.
- Aged 30 to 55 years.

- Stable periodontal condition and missing one single tooth (maxillary anterior teeth and premolars) with adjacent teeth present and thin mucosal phenotype (< 2mm bucco- lingual thickness).

Exclusion Criteria:

- Medically compromised patients and systemic conditions precluding periodontal surgery.
- Smokers.
- Severe hematologic disorders (e.g., hemophilia or leukemia), uncontrolled infectious or metabolic diseases that could compromise normal healing, liver, or kidney dysfunction/failure.
- Patients subjected to irradiation in the head and neck area.
- Patients treated or under treatment with intravenous amino bisphosphonates.
- Patient affected by active periodontitis or has poor oral hygiene and motivation.
- Uncontrolled diabetes mellitus.
- Pregnant women or planning to become pregnant, and nursing mothers.

The clinical study design:

1. Phase I therapy

- All patients will receive a comprehensive periodontal examination, oral hygiene instructions and they will be subjected to full mouth scaling, root planning (SRP) and polishing.
- Sites with occlusal trauma will be subjected to occlusal adjustment.
- One month following phase I therapy, patients who qualify the inclusion criteria for surgical procedures in terms of oral hygiene measures and compliance will be selected.

2. Surgical Phase

- The sites will be classified randomly by the sealed envelope technique into two treatment groups, 13 sites in each group.

Group 1 (Control Group)

Autogenous SCTGs + dental implants*.

Group 2 (Test Group)

ACM**+ dental implant

Prior to the initiation of study procedures, Peri-implant Mucosal Thickness (PMT) at three different heights (1, 3, and 5 mm apical from the mucosal margin) will be measured using a custom stent and an endodontic spreader. Following enrolment, each participant will be randomly assigned using the sealed envelope technique by a masked investigator, to one of two treatment groups: Control (implant placement with autogenous SCTG harvested from the palatal mucosa); or test (implant placement with ACM). Participant allocation will be withheld from the surgeon until shortly before the surgical visit.

At the baseline surgical visit, local anaesthetic will be administered; the buccal PMT will be measured and recorded. A periodontal probe (UNC-15) and an endodontic spreader will be gently inserted through the custom stent to the surface of the mucosa and the bone, respectively, at approximately 1, 3, and 5 mm apical to the estimated free mucosal margin, using the gingival zenith of the adjacent teeth as a reference. The difference

* Biodem implant - Germany

** BioXclude, USA

between the measurement from the stent to the mucosa (using the probe) and from the stent to the bone (using the endodontic spreader) as the PMT.

Mid-buccal keratinized mucosal width (KMW) at the edentulous site using a periodontal probe (UNC-15) will be recorded, as well.

Surgical procedure

First surgery

All patients will be premedicated with antibiotic prophylaxis (Augmentin 2,000 mg or Clindamycin 600mg), depending on the history of drug allergy, 1 hour prior to implant placement surgery. Clinical photographs will be taken prior to, during, and after surgery.

All surgical procedures will be performed under strict aseptic conditions and all patients will be injected with local anaesthesia (Articaine 4% 1:100 000 epinephrine).

Paracrestal incisions extended through the papillae on either side of the implant site will be made. Vertical releasing incisions will be made, when it is necessary, on each side of the implant to facilitate the planned advancement of the flap tissue to cover the grafts. A combination of full thickness and partial thickness flap design will be employed to create a recipient bed for the graft and the implant will be placed in an ideal position according to the cone beam CT (CBCT) scan.

Following baseline measurements, the implant will be placed according to the manufacturer's protocol, along with the provided cover screw. For the control group, a connective tissue graft will be harvested from the palatal mucosa. For the test groups, the ACM will be prepared according to the manufacturer's instructions and trimmed to appropriate size.

The grafts will be positioned over the coronal and buccal aspect of the alveolar ridge and secured to the recipient sites with non-absorbable sutures anchored in the buccal periosteum and the palatal flap, and then passively covered with the primary flap. The flaps will be sutured with multiple simple interrupted and double vertical loop sutures to achieve primary closure in all cases using non-absorbable sutures.

3. Postoperative Care

- Patients will be continued to take the same antibiotics for 7 days. They will be instructed to rinse twice daily with a chlorhexidine mouth-rinse (0.12%) during the first 2 weeks and to avoid brushing and interdental cleaning next to the treated area. They also will be told to avoid chewing on, or inflict any trauma, to the treated area.
- Patients will return to the clinic 7 to 14 days post-surgery for suture removal, Final crown cementation after 6 months.

4. Outcomes variables

- **The primary outcome** of interest will be to measure changes (in mm) in horizontal PMT on the buccal aspect of the edentulous alveolar ridge from baseline (BL) (implant placement and grafting) to (3 and 6 month) of post-surgical healing.
- Prior to surgery (baseline), at 3 and 6 month, impressions of the grafted sites will be taken including at least the two neighbouring teeth and using an Addition silicone impression material. Dental stone casts will be fabricated and optically scanned with a desktop 3D scanner. Digital models of each time-point per patient will be captured as stereolithography (STL) files. Subsequently, these STL files will be imported into a digital imaging software program for analysis of the volumetric changes in the grafted areas. The images of the baseline and

follow-up datasets will be superimposed and matched using the best-fit algorithm at the adjacent tooth surfaces. After definition of specific regions of interest, the software will calculate the volumetric, changes will be measured in mm, which corresponded to the mean distance between the three surfaces representing the evaluated time-points (BL, 3 and 6 month).

- The secondary outcome of interest will include change (in mm) in mid-buccal (KMW) in an apico-coronal direction. Assessment of wound healing at different post-surgical time points using a modified wound healing index that was introduced by Huang et al.,(18) which evaluates periodontal soft tissue wound healing with scores from 1 to 3. On this scale, wounds are scored at baseline of surgery and at 4,8,12,24 weeks post-operative.
- The modified wound healing index (MWHI) included three categories:
 - 1) Uneventful wound healing with no or minimal mucosal edema or erythema, and no suppuration or graft exposure.
 - 2) Normal wound healing with slight to moderate mucosal edema, erythema and/or graft exposure, but no suppuration.
 - 3) Poor wound healing with significant mucosal edema, erythema, graft exposure, and suppuration.
- Patient-reported outcome measures (PROMs): self-reported postoperative discomfort and overall satisfaction upon study completion using a 100-point visual analog scale (VAS) recorded at 1,3,7,15 days post operatively.

Statistical analysis:

Data will be collected and analysed using Statistical Package for Social Science (SPSS) program for statistical analysis. Data validation for entry

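### The effect size of 1.121 borrows a porcine collagen matrix's SD (0.16 mm) for the ACM arm without justification; power for 0.50 mm should be given as a range, 45% to 71% two-sided at 11 per arm

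*Combined protocol and SAP*

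**What the plan says.** In the combined protocol and SAP, the section Sample size calculation bases the minimum sample on an earlier trial of augmentation around implants "with a porcine collagen matrix (CM) versus the subepithelial connective tissue graft (SCTG) from the palate". In that trial the mean gain in buccal thickness at six months "was 0.30 ± 0.16 mm (CM) and 0.80 ± 0.61 mm (SCTG"). From these figures the plan takes a "standardized effect size in increase in the soft tissue thickness (primary outcome) of 1.121". With 80% power and a 5% significance level it arrives at "11 patients per group", raised to 13 per group for 10% dropout.

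Sidedness is not stated in words, but the equation printed under Software uses the normal deviate at α/2, which is the two-sided form.

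The test arm is ACM. No SD for ACM appears anywhere in the document, nor any argument that a collagen matrix should vary as ACM does. The introduction notes how little has been published on ACM and says that no study has compared it with the connective tissue graft (SCTG) at implant placement. The hypothesis, just before Aim of the work, is that "using ACM membranes will produce equivalent results in terms of PMT enhancement" relative to SCTG.

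**The concern.** The two SDs behind 1.121 differ almost fourfold (0.61 / 0.16 = 3.8). The smaller one makes the effect size look large, and it comes from a material that is not being tested here. If ACM results vary more between patients than the collagen-matrix results did, a 0.50 mm difference is a smaller standardized effect and the trial has less power than stated.

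A reader of the plan would take 80% power for 0.50 mm to be a property of this trial. A non-significant result could then be read as coming from an adequately powered comparison, and so as support for the hypothesis that the two grafts perform alike.

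**Working it through.** **Inputs from Sample size calculation.** Mean gains 0.30 mm (CM) and 0.80 mm (SCTG), difference 0.50 mm; SDs 0.16 and 0.61; α = 0.05; 80% power; 11 per group, 13 after dropout. **Assumptions made here.** The comparison is an unpaired t-test (Statistical analysis names no test), and the ACM SD lies between 0.16 and 0.61.

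**1. The plan's effect size.**
Pooled SD = √((0.16² + 0.61²)/2) = √((0.0256 + 0.3721)/2) = 0.446.
0.50 / 0.446 = 1.121. This reproduces the stated figure and shows that the 0.16 enters it.

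**2. The plan's sample size at 1.121.**
- One-sided 5% t-test (noncentral t): 11 per group, power 81.4%. This matches the plan.
- Printed two-sided equation: 2 × (1.960 + 0.842)² / 1.121² = 12.5, so 13 per group.
- Two-sided t-test (noncentral t): 14 per group.
- Dropout: 11 / 0.90 = 12.2, so 13 per group. This matches the plan.

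So 11 is recovered only with a one-sided test. Two-sided, the plan's own effect size gives 70.6% power at 11 and 78.3% at 13.

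**3. Power for 0.50 mm as the ACM SD varies, with the SCTG SD held at 0.61.**
Pooled SD = √((s² + 0.61²)/2) and d = 0.50 / pooled SD. Power comes from the noncentral t distribution with 2n − 2 degrees of freedom and noncentrality d√(n/2).

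| ACM SD (s) | Pooled SD | d | Two-sided, n = 11 | Two-sided, n = 13 | One-sided, n = 11 | One-sided, n = 13 |
|---|---|---|---|---|---|---|
| 0.16 (plan) | 0.446 | 1.121 | 71% | 78% | 81% | 87% |
| 0.30 | 0.481 | 1.040 | 64% | 72% | 76% | 82% |
| 0.45 | 0.536 | 0.933 | 55% | 63% | 68% | 75% |
| 0.61 (as SCTG) | 0.610 | 0.820 | 45% | 52% | 58% | 65% |

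Here n is patients analysed per arm: 11 is the plan's minimum, and 13 applies if nobody drops out. Simulation with unequal SDs agrees with the Student t figures to within about one percentage point. Welch's test is slightly lower: 67% and 76% at SD 0.16, 44% and 51% at SD 0.61 (two-sided, 11 and 13 per arm).

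**4. Separating the two causes at 11 per arm.**
- Sidedness alone, SD kept at 0.16: 81% to 71%.
- SD alone, 0.16 to 0.61: 71% to 45% two-sided, or 81% to 58% one-sided.

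**5. Difference detectable with 80% power, two-sided, SD 0.61 in both arms.**
The required d is 1.256 at 11 per arm and 1.145 at 13.
1.256 × 0.61 = 0.77 mm; 1.145 × 0.61 = 0.70 mm.

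**The case against.** The strongest defence is that the proxy is disclosed and understandable. The plan says openly that its figures come from a collagen matrix, and the introduction explains why ACM data are hard to find. Borrowing from a trial of another graft substitute is ordinary planning. That stands: using a proxy is not an error in itself. What is missing is a justification and a sensitivity range.

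A reader might infer that the trial's own hypothesis forces an ACM SD of 0.61 and hence 45% power. The documents do not support this. The hypothesis concerns the thickness gained and says nothing about spread between patients. Taken at its word it also implies a true difference near zero, so combining SCTG's SD with a 0.50 mm difference is a hybrid. The only SD that the documents pair with a 0.30 mm gain is 0.16. The 0.61 row is therefore a stress test at an assumed upper end.

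A reader might also infer that the stated 80% would hold if ACM were as uniform as the collagen matrix, and that the whole fall from 80% to 45% comes from the SD. Neither follows. Two-sided, power is 71% and 78% even at SD 0.16. The step from 81% to 71% at 11 per arm comes from sidedness.

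A one-sided reading softens the point: with all 13 per arm analysed, 80% is met at ACM SDs of 0.16 and 0.30. But the plan nowhere states a one-sided test, and its printed equation is two-sided. Under that reading the choice of SD still costs 23 points at 11 per arm (81% to 58%).

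Finally, a hypothesis of equivalence tested by a difference calculation with no margin is a larger mismatch. It is a separate matter and does not repair the power statement, which must stand on its own terms.

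**Conclusion.** The concern holds as a planning assumption that is neither justified nor tested for sensitivity. The effect size of 1.121 depends on an SD from a material outside this trial, and the ACM SD is unknown. Two-sided, the stated 80% for 0.50 mm is not reached at 11 or 13 per arm at any ACM SD from 0.16 to 0.61: power runs from 71% down to 45% at 11, and from 78% down to 52% at 13. At 11 per arm, the part attributable to the SD is up to 26 points two-sided (71% to 45%).

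These figures assume an unpaired t-test at 5%, the plan's 0.50 mm difference, an SCTG SD of 0.61, and an ACM SD within the range shown. An ACM SD outside that range would extend it. The low end is a possibility to disclose, not a prediction.

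**What to change.** Rewrite the paragraph in Sample size calculation without adding patients:

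- Say that the ACM SD is unknown and that 0.16 mm is borrowed from a porcine collagen matrix, with whatever reason the sponsor has for that choice.
- State whether the test is one- or two-sided and which n each power figure refers to.
- Replace the unqualified 80% and 1.121 with the power range for 0.50 mm. Two-sided at 11 and 13 per arm, this starts from 71% and 78% at the plan's own SDs and goes down to 45% and 52% at an assumed ACM SD of 0.61.
- Add that with SD 0.61 in both arms, the difference detectable with 80% power is about 0.77 mm (11 per arm) or 0.70 mm (13 per arm).

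The cost is one paragraph of wording and a less favourable power statement. Design, recruitment and procedures are unchanged.

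### The surgeon learns the arm before the surgical-visit PMT and KMW are read: opening the envelope after those readings, naming one pre-disclosure baseline and coding the STL files would cheaply remove an avoidable risk

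*Combined protocol and SAP*

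**What the plan says.** All references are to the combined protocol and SAP.

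- **Assignment and disclosure (2. Surgical Phase).** Participants are "randomly assigned using the sealed envelope technique by a masked investigator". The next statement is "Participant allocation will be withheld from the surgeon until shortly before the surgical visit".
- **PMT at the surgical visit (same section).** "At the baseline surgical visit, local anaesthetic will be administered; the buccal PMT will be measured and recorded". The probe reads to the mucosal surface and the spreader to bone, both through a stent.
- **KMW (end of the same section).** "Mid-buccal keratinized mucosal width (KMW) at the edentulous site using a periodontal probe (UNC-15) will be recorded, as well". The sentence names no visit. It directly follows the surgical-visit PMT description, and no other baseline KMW is described.
- **Earlier PMT (same section, before the assignment sentence).** "Prior to the initiation of study procedures, Peri-implant Mucosal Thickness (PMT) at three different heights" is to be measured. The Inclusion criteria also require "adjacent teeth present and thin mucosal phenotype", which calls for some thickness assessment by enrolment.
- **First arm-specific step (Surgical procedure, First surgery).** After the baseline measurements and implant placement, the arms part: "For the control group, a connective tissue graft will be harvested from the palatal mucosa", while the membrane is prepared in the test group.
- **Baseline and STL (4. Outcomes variables).** The primary outcome ties baseline to implant placement and grafting. The section also calls a pre-surgery impression baseline. Baseline and follow-up models are superimposed, regions of interest are defined and software computes the distances. Coding of the files is not mentioned.
- **Blinding (Study design).** The trial is described as single-blind without saying who is blinded. The only person called masked is the investigator who makes the assignment.

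**The concern.** The primary outcome and KMW are both changes from baseline. If whoever reads the baseline knows the arm, the reading can lean, even unintentionally, in a direction that depends on arm. Any such error that is not matched at follow-up goes directly into the between-arm difference. Randomisation does not remove it, because it arises after assignment.

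The stated hypothesis is that the two grafts give equivalent results. An error that shrinks the difference would therefore mislead as much as one that enlarges it.

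The exposure serves no purpose visible in the text, since the readings come before anything that depends on the arm. It also cannot be repaired later: once the site is grafted, the baseline cannot be read again.

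**Working it through.** **Step 1: order of events as written**

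| Order | Event | Does it need the arm? |
|---|---|---|
| 1 | PMT before study procedures | No |
| 2 | Envelope assignment | – |
| 3 | Arm disclosed to the surgeon, shortly before the visit | – |
| 4 | Surgical-visit PMT and, by text position, KMW | No |
| 5 | Incision, flap and recipient bed, implant | No difference by arm is described |
| 6 | Palatal harvest or membrane preparation | Yes |

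The pre-surgery impression cannot be placed in this order relative to disclosure. Swapping rows 3 and 4 costs no information needed at row 4. PMT is read from the mucosal surface to bone, which I take to mean intact mucosa, so the readings can be complete before the incision.

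**Step 2: which baseline is exposed**

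- PMT: exposed only if row 4 is the primary baseline. Tying baseline to implant placement and grafting points to row 4, but row 1 and the impression are also available and the plan does not choose.
- KMW: only row 4 is described, so the exposure does not depend on that choice.

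**Step 3: the plan's own figures (Sample size calculation)**

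- Pooled SD = √((0.16² + 0.61²)/2) = 0.446 mm.
- Effect size = (0.80 − 0.30)/0.446 = 1.121, as stated.
- A one-sided t-test at 5% gives power 0.778 at 10 and 0.814 at 11 per group, which reproduces 11. Then 11/0.9 = 12.2, so 13 after dropout. (The printed formula is two-sided and gives 12.49, so 13 before dropout. That is a separate matter.)

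**Step 4: illustration of size**

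The documents give no bias size, so the errors below are assumed.

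- Net error e = arm-related error at follow-up − arm-related error at baseline.
- With no true difference, the two-sided 5% t-test rejects with probability P(|T| > t₀.₉₇₅), where T is noncentral t with 2n − 2 degrees of freedom and noncentrality (e/SD)·√(n/2).
- Example: n = 11, e = 0.10 mm: (0.10/0.446)·√5.5 = 0.526 on 20 degrees of freedom, which gives 7.9%.

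| Net error (mm) | In SD units | 11 per group | 13 per group |
|---|---|---|---|
| 0 | 0 | 5.0% | 5.0% |
| 0.05 | 0.11 | 5.7% | 5.9% |
| 0.10 | 0.22 | 7.9% | 8.5% |
| 0.20 | 0.45 | 17.1% | 19.5% |

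At 11 per group and e = 0.10 mm, an assumed SD of 0.30 mm gives 11.6% and 0.61 mm gives 6.5%.

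**Step 5: the baseline alone is not enough**

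With assumed errors of 0.10 mm at 11 per group:

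- same sign at both visits: e = 0, 5%;
- one visit only: e = 0.10 mm, 7.9%;
- opposite signs: e = 0.20 mm, 17.1%.

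If same-sign errors had been cancelling, cleaning only the baseline would move the rate from 5% to 7.9%. The follow-up reading needs attention too.

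**The case against.** The strongest objection is that disclosure to the surgeon biases a reading only if the reader knows the arm, and nothing says the surgeon takes the readings. A masked examiner is neither stated nor excluded. This stands, and it limits the point to a risk. A reader might infer that the baseline will be read by someone who knows the arm; the documents do not support that.

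A second objection is that PMT already has a reading described before assignment. This also stands. A reader might infer that the primary baseline is compromised, but that would follow only if the surgical-visit reading were the one used. The argument that does not depend on this choice is the one for KMW, a secondary outcome, and even there the visit is inferred from the sentence's position.

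Third, a reader might infer from the order of sentences that the STL region is chosen after looking at the overlay. The text says only that regions are defined before the software calculates. Matching is algorithmic, and envelope timing has no shown route to a cast made before surgery. What remains is narrower: choosing a region is a human judgement, and neither coding nor a masked choice is described.

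Fourth, the figures rest on assumed errors. The SD pools 0.16 and 0.61 mm (variance ratio about 14.5) from a volumetric study of a different material, under an equal-variance test. They show scale and nothing more. KMW has no stated SD, so no millimetre error can be converted for it. The plan gives no equivalence margin, so I offer no equivalence figure.

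Finally, delaying disclosure until harvest could interfere with flap planning, since releasing incisions are made "to facilitate the planned advancement of the flap tissue to cover the grafts". I accept this: the envelope should be open before the incision.

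**Conclusion.** The point holds as a cheap improvement, with medium confidence. The plan discloses the arm to the surgeon before the surgical-visit PMT and the only described baseline KMW, although neither reading needs it, and it states no safeguard for the reader. It does not follow that any reading is biased, or that the primary analysis is invalid.

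The size cannot be obtained from the documents. With SD 0.446 mm, 11 per group and an assumed net error of 0.10 mm in the change score, a two-sided 5% error rate would become about 8%. The range is 5.7% to 17% for net errors of 0.05 to 0.20 mm. This assumes an equal-variance t-test and an error that differs by arm and does not cancel between visits. The sample size is unaffected.

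**What to change.** 1. In 2. Surgical Phase, replace the disclosure sentence with wording such as: *Allocation is disclosed to the surgeon only after baseline PMT and KMW have been recorded at the surgical visit, and before the incision.*
2. In 4. Outcomes variables, name one pre-disclosure reading as the primary baseline: the PMT taken before assignment, the surgical-visit PMT once item 1 is in place, or, if STL is the primary method, a pre-surgery impression taken before disclosure.
3. In the same section, state that STL files go to the analyst under codes that do not show the arm. State also that the region of interest is fixed on the baseline model, relative to the adjacent teeth, before any distance is viewed.

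If someone already on the team was not at the surgery, that person should read the 3- and 6-month PMT and KMW, because items 1 and 2 protect only the baseline half of the change score. No added reader is required.

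**Cost.** There is no extra procedure and no change in sample size. Materials for both arms must be ready at each surgery, and files must be relabelled. The fixed region must be large enough to contain the grafted area. Masking of clinical readings at follow-up will be partial, because the palatal donor site may be visible.

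### The first post-operative wound healing score is at week 4, so early events that resolve before then do not enter this secondary outcome, although patients already return at 7 to 14 days

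*Combined protocol and SAP*

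**What the plan says.** Section 4. Outcomes variables lists, among the secondary outcomes, "Assessment of wound healing at different post-surgical time points using a modified wound healing index". The schedule is: "wounds are scored at baseline of surgery and at 4,8,12,24 weeks post-operative".

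The index has three categories. The best is "Uneventful wound healing with no or minimal mucosal edema or erythema, and no suppuration or graft exposure" and the worst is "Poor wound healing with significant mucosal edema, erythema, graft exposure, and suppuration". The middle category, described as normal healing, allows slight to moderate edema, erythema and/or graft exposure, without suppuration.

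Section 3. Postoperative Care states: "Patients will return to the clinic 7 to 14 days post-surgery for suture removal". It assigns no wound score to that visit.

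Three other places bear on early healing:
- The introduction says that growth factors in the chorion matrix "promote periodontal regeneration and provide a natural environment for accelerated healing".
- Section 3 prescribes a "chlorhexidine mouth-rinse (0.12%) during the first 2 weeks", with no brushing next to the treated area.
- Section 4 collects patient-reported outcomes "using a 100-point visual analog scale (VAS) recorded at 1,3,7,15 days post operatively".

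**The concern.** Edema, erythema and suppuration are chiefly early post-surgical signs, and graft exposure can also occur early. An index built on them, with nothing recorded between surgery and week 4, cannot register an exposure or a suppuration that arises and clears in that interval. Nor can it separate a wound that settled in 10 days from one that settled in 25: both would score the same at week 4.

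This matters because the introduction's case for the membrane includes faster healing, and the purpose stated just before the Aim of the work includes comparing soft tissue healing between the two grafts. The text supplied has no adverse-event section that would otherwise record early exposure or suppuration. Once the suture-removal visit has passed, the score cannot be recovered.

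**Working it through.** The plan states no figure for this outcome, so the check is of the schedule, followed by a test of whether its effect on power can be sized.

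**Schedule, in days after surgery**

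| Item | Section | Days |
|---|---|---|
| Wound healing index | 4. Outcomes variables | 0, then 4×7 = 28, 8×7 = 56, 12×7 = 84, 24×7 = 168 |
| Suture-removal visit | 3. Postoperative Care | 7 to 14 |
| Chlorhexidine rinse, no brushing at the site | 3. Postoperative Care | first 14 |
| Patient-reported VAS | 4. Outcomes variables | 1, 3, 7, 15 |

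1. No index score falls on days 1 to 27.
2. The suture-removal visit lies wholly inside that gap.
3. The period of protected wound care and all four VAS days lie in the same gap. Early recovery is thus recorded by the patient but not graded by a clinician.
4. A score at the existing visit would bring the first post-operative reading forward from day 28 to day 7–14, that is, by 28 − 14 = 14 to 28 − 7 = 21 days.
5. No section gives a reason for starting at week 4.

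**Can the effect on power be sized?** The documents give no score distributions, so every distribution below is an assumption. Each row shows the shares scoring 1/2/3 in the two arms. Power is simulated for a two-sided Mann-Whitney test at 5%, with the 13 per group from Sample size calculation and 20,000 runs.

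| Assumed time | One arm | Other arm | Power |
|---|---|---|---|
| Day 7–14 | 80/20/0% | 35/60/5% | about 68% |
| Day 7–14 | 80/20/0% | 50/45/5% | about 39% |
| Day 7–14 | 80/20/0% | 60/40/0% | about 19% |
| Day 7–14 | 10/90/0% | 5/90/5% | about 5% |
| Week 4 | 98/2/0% | 90/10/0% | about 3% |
| Week 4 | 100/0/0% | 85/15/0% | about 12% |
| Week 4 | 95/5/0% | 60/40/0% | about 60% |

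The early range (about 5% to 68%) and the week-4 range (about 3% to 60%) overlap almost entirely. Power follows the size of the assumed difference, not the visit day as such. An exact Fisher calculation on the share scoring 2 or 3, also with 13 per group, behaves the same way: about 69% for 70% v 20%, 46% for 60% v 20%, 5% for 20% v 5%, and under 1% for 10% v 2%. If the arms have nearly converged by week 4, a difference is almost undetectable then, but the documents do not say whether they will have.

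**The case against.** The strongest reply is that the documents nowhere say early healing is when the grafts differ. That stands: it is an inference from the index items, the two weeks of wound care, the early VAS days and the healing rationale. Graft exposure could persist or appear later, and weeks 4 to 24 would then detect it.

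An early score also has weaknesses of its own. The visit window spans a week in which edema and erythema may change quickly, and recording the day does not remove that spread with 13 per arm. Only the control arm has a palatal harvest, and the donor wound is likely to be more visible at 7 to 14 days than at week 4. The trial is single blinded and names no scorer for the index, so masking may be harder. These points qualify the early score but do not remove the reason to collect it.

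The early VAS gives some comparison of recovery, but discomfort does not substitute for graded exposure or suppuration.

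A reader might infer three stronger conclusions, which the documents do not support:
- **That the outcome will show a ceiling effect, or that an early score would restore power.** There are no data for either, and the assumed distributions above can produce either answer.
- **That a null healing result would wrongly support the equivalence hypothesis.** That hypothesis is stated in terms of mucosal thickness.
- **That the baseline score is worthless and should go, or that the early score must be the main comparison.** Baseline of surgery is not defined, and a reading then could document the starting condition of the mucosa. Both choices are matters of preference.

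**Conclusion.** The concern holds in a limited form. It is certain from the text that the index has no score on days 1 to 27, that a planned visit lies inside that gap, and that no reason is given. It follows directly that exposure or suppuration resolving before week 4 does not enter this outcome. That a difference in early healing speed could be missed is plausible on the plan's own rationale but not demonstrated.

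The effect is confined to one secondary outcome. The primary mucosal thickness outcome and the sample size are untouched. The measurable change is in timing, with the first post-operative score 14 to 21 days earlier. This is a low-cost improvement worth making, not a flaw that invalidates the comparison.

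**What to change.** In 4. Outcomes variables, add the existing suture-removal visit to the scoring times of the index, with the actual post-operative day recorded. Report that score by group alongside weeks 4, 8, 12 and 24. If the sponsor prefers to start at week 4, the protocol should give the reason.

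The cost is one further entry on the case report form at a visit that is already planned, with no new visit or procedure and no change to treatment. Two limits should be acknowledged in the report: the one-week spread in timing, and the chance that a visible palatal donor wound reveals the allocation. The protocol should state who scores the index and whether that person is masked. The change should be made before enrolment, or as early as possible, because missed early scores cannot be recovered.
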